2.4.2. Change in e-GFR

[Analysis Target]

Cases subject to efficacy analysis

Cases with one measurement date at baseline and before baseline are classified as the pre-administration group, and cases with one or more measurement dates during administration are classified as the post-administration group.

Analyses targeting cases that apply to either the pre-administration group or the post-administration group (however, excluding cases that only have two points: one at baseline and one either before baseline or during administration) will be conducted.

[Analysis Method]

- 1) e-GFR will be treated as the dependent variable using actual values, and a linear mixed-effects model will be applied as repeated measurement data. The explanatory variables of the model are the administration group, time (years), patient, interaction of administration group and time, and interaction of patient and time as fixed effects, and the intercept and slope of the straight line over time for each patient as random effects. The variance-covariance matrix of the random effects will be unstructured.
- 2) The change in e-GFR from before baseline to baseline for the pre-administration group, and the change in e-GFR from baseline to after baseline for the post-administration group will be calculated. The change in e-GFR will be calculated using the following formulas:
 - Pre-administration change = (Pre-baseline value Baseline)
 - Post-administration change = (Post-administration value Baseline)

In addition, the Estimated Slope and Estimated SE will be calculated separately for the preadministration group and the post-administration group. The difference in the Estimated Slope between the pre-administration group and the post-administration group and its test result will be displayed as the estimated parameter values based on the solution of the fixed effects of the administration group and time, and the p-value based on the t-distribution.

Reference

- 1. Marc Froissart, Jerome Rossert, Christian Jacquot, Michel Paillard and Pascal Houillier: Predictive performance of the modification of diet in renal disease and Cockcroft-Gault equations for estimating renal function. J Am Soc Nephrol 16: 763-73, 2005.

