Cases excluded from efficacy analysis	Among the cases subject to safety analysis, cases that fall under the following items. 1) Cases where the purpose of use is not "suppression of ADPK progression with a rapid kidney volume increase in patients with increase kidney volume" 2) Cases where the efficacy evaluation items have not been measured after the administration of the drug, or there is no efficacy data measured with the allowable range at each evaluation time	
Cases subject to efficacy analysis	Among the cases subject to safety analysis, cases excluding those excluded from the efficacy analysis.	

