1.4.2. Significance Level and Confidence Interval of the Test

The significance level of the test is set at a two-tailed 5%, and the confidence level of the confidence interval is set at a two-tailed 95%.

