2.4. Aggregation Regarding Efficacy

2.4.1. Rate of Change in Bilateral Total Kidney volume

[Analysis Target]

Cases subject to efficacy analysis

Cases with one measurement date at baseline and before baseline are classified as the pre-administration group, and cases with one or more measurement dates during administration are classified as the post-administration group.

An analysis will be conducted on cases that fall into either the pre-administration group or the post-administration group.

[Analysis Method]

Regarding the rate of kidney volume increase

1) To reduce heterogeneity of variance and achieve linearity over time, the data of bilateral total kidney volume is log-transformed (log10). This log-transformed bilateral total kidney volume is set as the dependent variable, and a linear mixed-effects model is fitted as repeated measures data. The explanatory variables of the model are the administration group, time (years), patient, interaction of administration group and time, and interaction of patient and time as fixed effects, and the intercept and slope of the time axis for each patient as random effects. The variance-covariance matrix of the random effects is unstructured. The annual change rate and 95% confidence interval are returned to

their original scale by (10 estimated value -1) x 100.

Time (years) is calculated as "(measurement date - baseline +1) \div 365.25".

- 2) The pre-administration group calculates the rate of kidney volume change from before the baseline to the baseline, and the post-administration group calculates the rate of kidney volume change from the baseline to after the baseline. The rate of change in kidney volume is calculated using the following formula.
 - Rate of kidney volume change = {((post-administration value pre-administration value) / pre-administration value) x 100} / "period (years) from the start of administration of this drug to the measurement date"

Also, the Estimated Slope and Estimated SE are calculated for each of the pre-administration group and the post-administration group, and a graph is created. The difference in the Estimated Slope between the pre-administration group and the post-administration group and its test result are displayed as the estimated value of the parameter based on the solution of the fixed effect of the administration group and time and the p-value based on the t-distribution.

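### The e-GFR analysis drops every patient with only a baseline and one other value: an unexplained selection on post-baseline data that can bias the change summary, and possibly the slope, in an unknown direction

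*SAP*

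**What the plan says.** SAP 2.4.2 sets the e-GFR analysis population in its Analysis Target block. A patient joins the on-drug side with a single value: "cases with one or more measurement dates during administration are classified as the post-administration group". The same block then narrows the set, "excluding cases that only have two points: one at baseline and one either before baseline or during administration". Because the clause sits there, it governs both methods that follow: the mixed model in 1) and the simple change from baseline in 2).

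The model in 1) lists patient effects twice: "interaction of patient and time as fixed effects, and the intercept and slope of the straight line over time for each patient as random effects". What is reported is a pre/post contrast: "The difference in the Estimated Slope between the pre-administration group and the post-administration group and its test result will be displayed".

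Two other places bear on the clause. SAP 2.4.1 uses the same group definitions and model structure for kidney volume and does not narrow the set: "An analysis will be conducted on cases that fall into either the pre-administration group or the post-administration group". SAP 1.2 already removes from the efficacy set "Cases where the efficacy evaluation items have not been measured after the administration of the drug".

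No reason is given for the e-GFR clause. SAP 2.1.1 plans a list only for exclusions from the safety and efficacy sets, so patients lost through this clause would not appear in it.

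**The concern.** The clause names both two-point patterns, but it probably does not fall on them equally. After the efficacy-set filter, a patient with a baseline and one earlier e-GFR value remains only if the on-drug efficacy item was kidney volume alone. Most of those removed should therefore have a baseline and one on-drug value, so inclusion depends on how many measurements followed the start of treatment.

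Take two patients with the same baseline and the same single on-drug value. If one also has an older e-GFR value, that patient has three points and stays; the other is dropped. Yet both supply a complete change from baseline for method 2), and no modelling argument applies to that summary.

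The survey has no control arm, so the e-GFR result rests on a pre/post contrast. If the number of on-drug measurements is related to the rate of decline, removing the two-point patients changes the on-drug side. It also makes the two efficacy results rest on different patients for no stated reason.

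**Working it through.** **Inputs.** From the documents: 1,600 planned patients, the clause, the group definitions and the model. Not in the documents: the two-point share, e-GFR slopes, SDs, visit spacing and pattern of loss. All of these are assumed below. The plan states no figure to reproduce. Units are mL/min/1.73m², per year for slopes.

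**Step 1: change from baseline (method 2).** Assume a mean slope of -3.5 with SD 2.5. Let *f* be the two-point share, and let the faster-declining half of patients be *r* times as likely as the slower half to have two points. The two-point probability is *a* = 2*f*/(1+*r*) in the slower half and *ra* in the faster half. The half means lie 2.5 × √(2/π) = 1.995 either side of the overall mean. At a visit *t* years after start, the retained mean change minus the all-patient mean change is

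*t* × 1.995 × (*r*-1)*a* / (2-2*f*)

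| *f* | *r* | *a* | Shift at 1 year | Shift at 6 months |
|---|---|---|---|---|
| 0.12 | 3 | 0.06 | 1.995 × 0.12/1.76 = +0.14 | +0.07 |
| 0.20 | 3 | 0.10 | 1.995 × 0.20/1.60 = +0.25 | +0.12 |
| 0.30 | 5 | 0.10 | 1.995 × 0.40/1.40 = +0.57 | +0.29 |

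Simulations with these inputs agree: +0.14 to +0.59 at 1 year and +0.08 to +0.28 at 6 months; a separate run gave 0.08 to 0.49. If slower decliners are the ones with two points, the sign reverses (-0.25 at 1 year for *f* = 0.20). If loss is random, the shift is zero. Keeping the two-point patients removes the shift at the visit where their value falls. It cannot help at later visits, where they have no value.

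**Step 2: slope, patient intercept and slope random.** Intercept SD 20, slope SD 2.5, residual SD 3, true slope -3.5, single on-drug value at 1 year, faster decliners 3 to 5 times as likely to have two points:

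| Two-point share | Slope, all kept | Slope, two-point excluded | Due to the clause |
|---|---|---|---|
| 12% | -3.39 | -3.33 | +0.06 |
| 20% | -3.32 | -3.24 | +0.08 |
| 30% | -3.14 | -2.94 | +0.20 |

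Repeat runs gave +0.04 to +0.23 with the value at 1 year and +0.02 to +0.07 at 6 months, about 0 under random loss, and -0.04 to -0.09 if slower decliners leave early.

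A second simulation used 1,600 patients, a pre slope of -4, an on-drug slope of -3, slope SD 2 and residual SD 4. Entries are the post-administration slope with two-point cases excluded minus kept:

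| Scenario | 8-10% two-point | 37% two-point |
|---|---|---|
| Random loss | 0.000 | -0.001 |
| Faster decliners leave early | 0.000 | +0.018 |
| Slower decliners leave early | -0.002 | -0.029 |
| One-off on-drug fall of 3 units, random loss | +0.013 | +0.184 |
| One-off on-drug rise of 3 units, random loss | -0.014 | not run |

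In the largest of these (+0.184), the pre/post slope difference moved by +0.154 against an SE of 0.188.

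**Step 3: slope, patient and patient-by-time fixed.** Two points are fitted exactly by the patient's own intercept and slope, so the patient adds nothing to the group-by-time estimate. With and without two-point patients, that estimate agreed to six decimals in every scenario.

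**The case against.** A reader might infer that the clause makes the drug look better by 0.2 to 0.6 per year. The documents do not support that.

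- **Direction.** There are no e-GFR data and no pattern of discontinuation from which to fix a sign. The sign follows whatever is assumed about who has few measurements.
- **Size.** The distance from -3.5 to the excluded-set slopes in step 2 is 0.17, 0.26 and 0.56. Most of that comes from informative loss and stays when everyone is kept (0.11, 0.18 and 0.36). The clause's own part is about one third.
- **Short follow-up.** The rule counts measurements, not time. In the second simulation the median time of the single value was 0.25 years with regular visits and 1.58 years with sparse sampling.

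Two further arguments carry weight. First, with patient effects literally fixed, the clause has no effect on the reported slope contrast. That stands, but the SAP also lists these effects as random, so which model will run is unclear, and method 2) is affected either way. Second, exclusion can help. With an assumed one-off on-drug fall of 3 units, random loss and the single value at 6 months, excluding two-point cases moved the slope towards the true -3.5: from -3.92 to -3.86 at a 12% share, and from -4.12 to -3.92 at 30%. So a favourable shift is not always bias.

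A different rule for a different endpoint is not in itself an error. Here, though, no reason is given. The clause also does not remove patients with a lone on-drug value, but these carry no slope information, so keeping them is harmless.

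**Conclusion.** The concern holds in limited form. The clause is unexplained, differs from the kidney-volume analysis, and probably selects the e-GFR set on post-baseline data; the last point is an inference from the efficacy-set definition.

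The firmer consequence is in method 2), where complete changes from baseline are discarded. Under informative loss, the mean change at the visit concerned shifts by roughly 0.1 to 0.6 mL/min/1.73m², in either direction. The slope is affected only if patient effects are random, and then probably by about 0.2 per year or less; it was at most about 0.015 in the second simulation when 8-10% of patients had two points. Under random loss, with no one-off on-drug change, both effects vanish. Every size rests on assumed shares, slopes and loss patterns.

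**What to change.** Delete the exclusion in SAP 2.4.2, so that every patient with a baseline and at least one other e-GFR value enters both the change summary and the mixed model. State that patient intercept and slope are random effects, and remove patient and patient-by-time from the fixed effects. Report the number of two-point cases by pattern (baseline plus one earlier value; baseline plus one on-drug value). Show the fit restricted to three or more points as a sensitivity analysis.

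The cost is one deleted clause, one clarified model sentence, a short table and a second model run, with no new data. With random patient effects and no informative loss, keeping these patients gives a slightly smaller SE. One small downside: if e-GFR makes a one-off change soon after starting the drug, two-point cases give that change more weight in the slope. The sensitivity fit would show it.

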Study ID: I15600-003

Samsca drug use-results survey (ADPKD) Study Protocol

NCT Number: NCT02847624

Otsuka Pharmaceutical Co., Ltd.

Protocol Creation Date: February 21, 2014, Version 1.0 Date of the latest version: September 2, 2021, Version 8.0

Objective of	To determine the safety and efficacy of Samsca used in routine clinical settings for suppression of
survey	ADPKD progression.
Survey	<all patients="" survey=""></all>
methods	All patients treated with Samsca must be registered in the survey until "CONDITIONS FOR
	APPROVAL" is removed.
	CRFs must be collected from all patients until the total number of patients registered in the survey
	reaches the planned number.
	Observation period: From start of Samsca administration through the end of survey
	In case of finish or discontinue of Samsca administration, collecting information of kidney
	volume, changes in renal function and hepatic dysfunction (outcome: not recovered) through
	the end of survey (8 years).
Survey period	8 years (March 24,2014 ~ March 23,2022)
Planned	1,600
number of	Depending on the onset of significant drug-induced liver injury post-marketing, the planned
patients to be	number of patients will be re-evaluated and necessity of additional safety measures will be also
surveyed	assessed.
	In addition, if there is a substantial change in expected number of patients with long-term
	treatment (≥4 years), the planned number of patients will be re-evaluated so as to collect at least
	800 patients with long-term treatment.
Target patient	All patients treated with Samsca after March 24, 2014 for the indication of "suppression of
population of	ADPKD progression with a rapid kidney volume increase in patients with increased kidney
• •	volume"
Major items to	1
	CRFs of drug use-results survey (for treatment period) 1) Patient information
be surveyed	
	Patient initials (last name, first name), patient ID, sex, any breast feeding, any pregnancy,
	date of birth (age), date of informed consent received (in written form)
	2) Patient demographics
	Indication for use, time of ADPKD diagnosis, diagnosis of ADPKD (severity of ADPKD,
	family history, number of cysts, complications (especially, hepatic cyst, pancreatic cyst,
	cerebral aneurysm, urinary calculus, any complication of cyst infection), past history,
	predisposition to hypersensitivity, history of drug adverse reactions
	3) Administration status of Samsca

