1.3. Evaluation Period and Evaluation Range

The following formula is used to calculate the number of days.

Number of days = [Observation Day] - [Start Day of Administration] + 1 (The same day is considered as the first day)

Furthermore, the pre-administration value adopts the "start date of administration". However, if there is no data for the "start date of administration", the data closest to the start date of administration will be adopted. This pre-administration value is used as the baseline.

The "clinical test values" and "progression of renal function, etc." will adopt the data from the final volume and final SEQ if there is the same date among the data with test values.

Evaluation Period	Standard Number of Days	Permissible Range
Pre-administration	One day before the start of	Within 0 days
	administration	
Start date of administration	Start date of administration	Day 1

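### SAP 2.4.2 item 2) leaves the e-GFR changes before and after starting Samsca without a time unit and in opposite time directions, so the two descriptive figures are not comparable

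*SAP*

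**What the plan says.** SAP 2.4.2 treats e-GFR in two ways.

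- **Item 1)** fits a linear mixed model to the measured values. Its terms begin: "The explanatory variables of the model are the administration group, time (years), patient, interaction of administration group and time". The test comes from this model: "The difference in the Estimated Slope between the pre-administration group and the post-administration group and its test result will be displayed", with a p-value from the t-distribution.
- **Item 2)** calls for "The change in e-GFR from before baseline to baseline for the pre-administration group, and the change in e-GFR from baseline to after baseline" in the post-administration group, and defines a per-patient change for each group: "Pre-administration change = (Pre-baseline value Baseline" and "Post-administration change = (Post-administration value Baseline". The operator between the two terms does not appear in the readable text, and I take it as a minus sign. Neither formula has a divisor.

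The parallel kidney-volume formula, SAP 2.4.1 item 2), is a percentage change divided by the "period (years) from the start of administration of this drug to the measurement date".

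SAP 1.3 ties baseline to the "start date of administration", or to the nearest value if that day has none. It gives no look-back window for an earlier e-GFR value. The 92-day limit in SAP Table 1 applies only to pre-administration kidney volume. The protocol gives the survey period as "8 years (March 24,2014 ~ March 23,2022" and observes patients from first dose to the end of the survey.

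**The concern.** The protocol's items to be analysed name two efficacy topics, kidney volume and e-GFR. The SAP expresses the per-patient kidney-volume change per year and leaves the e-GFR change as a raw difference, without giving a reason.

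If e-GFR is falling, the size of a raw change depends on how long the patient was observed as well as on how fast function was lost. On-drug follow-up can reach 8 years, and the protocol wants at least 800 patients treated for 4 years or more. The pre-baseline interval is whatever the records supply.

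The two formulas also run in opposite time directions. A loss before treatment prints as a positive number and a loss after it as a negative one. A reader taking the signs at face value would see e-GFR rising before Samsca and falling on it, even if the rate never changed.

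**Working it through.** **Inputs from the documents**
- The two change formulas (SAP 2.4.2 item 2).
- The survey dates (protocol). 24 March 2014 to 23 March 2022 inclusive is 8 × 365 + 2 leap days = 2,922 days, and 2,922 / 365.25 = 8.0 years. The stated 8 years is reproduced and is the longest possible on-drug interval.

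**Assumed inputs, not in the documents**
- A constant decline d of 3 mL/min/1.73m² per year, with 1 and 5 as the range.
- A pre-baseline interval Tpre of 0.25 to 5 years.
- A post-baseline interval Tpost of 1, 4 or 8 years.

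**Formulas.** Let B be the baseline value.
- The earlier value is B + d × Tpre, so the printed pre change is +d × Tpre.
- The later value is B - d × Tpost, so the printed post change is -d × Tpost.
- The ratio of sizes, post to pre, is Tpost / Tpre, whatever d is.

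**Results for an unaltered decline of 3 per year**

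| Tpre (years) | Tpost (years) | Pre change as printed | Post change as printed | Ratio of sizes |
|---|---|---|---|---|
| 0.25 | 8 | +0.75 | -24 | 32 |
| 1 | 8 | +3 | -24 | 8 |
| 1 | 4 | +3 | -12 | 4 |
| 1 | 1 | +3 | -3 | 1 |
| 5 | 8 | +15 | -24 | 1.6 |
| 5 | 1 | +15 | -3 | 0.2 |

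At 1 or 5 per year the ratios are the same. With 1 year before and 8 years after, the printed values become +1 and -8, or +5 and -40.

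**A real benefit can be hidden.** If the decline halves to 1.5 per year on drug, 5 years gives 1.5 × 5 = 7.5 lost, against 3 × 1 = 3 in a 1-year pre interval. The raw loss is 2.5 times as large although the rate is half.

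**After the fix.** Later minus earlier, divided by elapsed years, gives (-d × Tpre) / Tpre = -d before and (-d × Tpost) / Tpost = -d after. At d = 3 that is -3.0 per year on both sides, for any intervals.

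**Does the slope test share the problem?** A slope is already per year, so interval length does not scale it. One simulated data set agrees (400 patients, 11 records each, true slope -3 throughout, random intercept and slope). The estimated slope difference was -0.21 per year (SE 0.21, p = 0.32). In the same data the item 2) changes averaged +2.84 over 1 year before and -24.65 over 8 years after. Put in time order and divided by years, these are -2.84 and -24.65 / 8 = -3.08. The simulation left out the fixed patient and patient-by-time terms that the SAP also lists, and a single run is a consistency check only.

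**The case against.** The strongest reply is that 2.4.2 already contains the time-standardised comparison. The mixed model gives a slope and standard error for each group and tests their difference. Item 2) is descriptive, no test of one raw change against the other is specified, and no side-by-side table is laid out. A raw change from baseline alongside annual slopes is a recognisable choice, and the section title promises a change, not a rate. This stands, and it limits how much the point matters. It does not make the two changes comparable, and item 2) still defines them as a pair.

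Three stronger readings are tempting, and the documents do not support them.

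- **The raw changes must make function look worse after starting.** This needs a short pre-baseline interval, and no interval is given. With 5 years before and 1 year after, the ratio is 0.2 and the distortion reverses.
- **Post changes certainly mix months with 8 years.** SAP 1.2 excludes patients without efficacy data inside a permitted window at the evaluation times, which suggests scheduled times. The table in 1.3 shows only two rows as readable and may be incomplete, so a by-visit layout of post changes cannot be ruled out. Even so, a pre change over an unstated interval would have no matching post column.
- **The efficacy test is biased by this.** It uses annual slopes, which do not carry the interval-length effect.

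A fair criticism of the remedy is that a two-point difference over a very short interval is noisy when annualised. At 0.1 year, measurement error is multiplied by 1 / 0.1 = 10.

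**Conclusion.** The point holds for the descriptive summary in 2.4.2 item 2) and no further. The two e-GFR changes have no time unit, the pre-baseline interval is unstated, and the pre formula is reversed in time. With no change in the rate of decline, the sizes differ by the factor Tpost / Tpre, which is 8 for 1 year before and 8 years after, and 0.2 for 5 years before and 1 year after. The signs are opposite in every case. Neither the size nor the direction of the distortion can be predicted from the plan.

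The factor assumes a constant decline but does not depend on its rate. The printed values of +3 and -24 do depend on the assumed 3 per year, and the signs depend on reading the missing operator as a minus. The correction should be made, but the formal pre/post inference does not depend on it.

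**What to change.** In SAP 2.4.2 item 2):

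1. Define both changes as (later value - earlier value) / years between the two measurement dates, in mL/min/1.73m² per year. This puts e-GFR on a per-year footing like kidney volume and corrects the pre formula's direction. Use the gap between the two measurements; the 2.4.1 divisor counts from the start of the drug and does not describe a pre-baseline interval.
2. State which pre-baseline and post-baseline values are used when a patient has several.
3. Report the distribution of interval lengths beside the per-year values, so that noise from very short intervals is visible.
4. If the raw post change is also wanted, show it by year on drug and not against the pre change.
5. State that pre/post inference rests on the mixed-model slopes.

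The cost is SAP wording and one derived variable. The mixed model needs time in years, so the measurement dates are already required.

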Items to be CRFs of drug use-results survey (for treatment period) analyzed 1) Items related to constitution of patients Number of patients enrolled, number of patients withdrawn, number of CRFs collected, number of patients excluded, number of patients analyzed for safety, number of patients analyzed for efficacy 2) Items related to efficacy Changes in kidney volume data, changes in renal function test data (e-GFR) 3) Items related to safety (1) Safety in elderly patients (2) Safety of Samsca in advanced ADPKD patients (creatinine clearance <60 mL/min) (3) Adverse events of special interest (hepatic dysfunction, increases in transaminases (AST or ALT)) (4) Items to be closely monitored: hepatic dysfunction (5) Safety of Samsca in ADPKD patients after long-term treatment CRFs of drug use-results survey (for follow-up period) 1) Changes in kidney volume, changes in renal function test data (e-GFR)

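### SAP 2.4.2: the formula for the pre-administration e-GFR change is reversed against its own definition, so the descriptive change has the wrong sign; the slope test is unaffected

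*SAP*

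**What the plan says.** Item 2 of the Analysis Method in SAP 2.4.2 defines two changes in one sentence. The first is "The change in e-GFR from before baseline to baseline for the pre-administration group" and the second is "the change in e-GFR from baseline to after baseline for the post-administration group will be calculated". Both run forward in time.

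Two formulas follow. One begins "Pre-administration change = (Pre-baseline value" and the other begins "Post-administration change = (Post-administration value". In each, Baseline is the second term.

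Item 1 of the same section specifies a linear mixed-effects model in which "e-GFR will be treated as the dependent variable using actual values". After item 2, the section says: "The difference in the Estimated Slope between the pre-administration group and the post-administration group and its test result will be displayed". No test of the item 2 changes is specified.

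SAP 2.4.1 words the corresponding kidney volume quantity in the same forward direction: "The pre-administration group calculates the rate of kidney volume change from before the baseline to the baseline". The protocol's efficacy items are "Changes in kidney volume data, changes in renal function test data (e-GFR"), so e-GFR change is one of only two.

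**The concern.** A change that starts at the pre-baseline measurement and ends at baseline is Baseline minus Pre-baseline value. The formula has the terms the other way round. Two conflicts follow within one section:

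- The pre-administration formula contradicts the sentence that introduces it.
- It subtracts later from earlier, while the post-administration formula subtracts earlier from later.

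The documents describe no parallel control group, so efficacy is read by setting the period before the drug against the period on it. A reversed sign in one period matters for that reading. Steady decline would appear as a gain before the drug and a loss on it, which could be taken as worsening on treatment. The pre-administration change would also disagree in sign with the pre-administration Estimated Slope reported in the same section.

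**Working it through.** The plan states no figure on this point, so there is none to reproduce. The check is of the order of the terms, followed by illustrations.

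**Inputs from the SAP.** The two definitions and two formulas come from 2.4.2, item 2. The minus signs do not show in the text available for this review, which is a PDF-reading loss and not a fault of the plan. The order of the terms is legible, and subtraction is the only operation that yields a change.

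**Side by side.**

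| Period | Defined direction | Change as defined | Formula in the SAP | Agree? |
|---|---|---|---|---|
| Pre-administration | earlier to baseline | Baseline − Pre-baseline | Pre-baseline − Baseline | No, sign reversed |
| Post-administration | baseline to later | Post − Baseline | Post − Baseline | Yes |

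**General case.** Let e-GFR(t) = a − d·t, with baseline at t = 0 and decline d per year.

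- Pre, by the SAP formula: e-GFR(−t_pre) − e-GFR(0) = +d·t_pre
- Pre, as defined: −d·t_pre
- Post, by either: −d·t_post
- Post minus pre, by the SAP formulas: −d·(t_pre + t_post)
- Post minus pre, as defined: d·(t_pre − t_post), which is 0 for equal windows

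**Illustrative sizes.** The documents give neither rates of decline nor interval lengths, so every d and window here is an assumption. With one-year windows:

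| Assumption | Pre (SAP formula) | Post | Post − pre (SAP formulas) | Post − pre (as defined) |
|---|---|---|---|---|
| d = 2, unchanged | +2 | −2 | −4 | 0 |
| d = 5, unchanged | +5 | −5 | −10 | 0 |
| d = 2, halved to 1 on drug | +2 | −1 | −3 | +1 |
| d = 5, halved to 2.5 on drug | +5 | −2.5 | −7.5 | +2.5 |

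In the last two rows the apparent direction of the drug's effect is reversed. The SAP does not define the post-minus-pre difference. It is shown here as what a reader would infer from comparing the two changes.

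**Single patients (assumed values).** Values of 60, 56 and 53 give +4 and −3 by the SAP formulas, against −4 and −3 as defined. Values of 58, 60 and 58 (a rise, then a fall) give −2 and −2 by the SAP formulas, against +2 and −2 as defined, so the reversal in course disappears.

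**Does the slope test use these formulas?** No. The model takes e-GFR values, time, group and patient; no change score enters it. A simulation of 300 patients, with assumed slopes of −4 per year before and −3 after, illustrates this. The mean one-year pre-administration change was +4.23 by the SAP formula and −4.23 as defined, with −2.84 after. The fitted pre-administration slope was −4.04 and the slope difference +1.04 per year, with neither change formula used. The simulated model had group, time and their interaction with random intercept and slope. It omitted the SAP's fixed patient and patient-by-time terms.

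**The case against.** The strongest reply is that both formulas share one form, measured value minus baseline, so the plan may intend a difference from baseline in both periods. On that reading the sentence, and not the formula, is the loose part. This is a plausible account of how the formula arose, and it is fair to say that calling the sign wrong takes the sentence as governing. It does not remove the conflict. The formula still contradicts the sentence, nothing tells the reader that the sign flips before baseline, and the result opposes the slope reported in the same section.

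A second reply is that the 2.4.1 formula does not clearly support a forward reading. Its labels do not fit a pre-baseline pair. If its time divisor is signed, which is an assumption, a value-minus-baseline numerator would still give a forward rate. That stands. Support from 2.4.1 rests on its sentence, not its formula.

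A third is that the quantity is descriptive and untested, that the sizes above are assumed, and that the SAP does not say the changes and slopes will be tabulated together. All of that is correct. It limits the consequence but leaves the contradiction in place.

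**Conclusion.** The concern holds. As written, the formula gives the exact negative of the pre-administration change that the SAP defines, for every patient whose e-GFR changed, and nothing elsewhere in the documents resolves it. The sign reversal needs only two things: reading the lost operator as a minus, and taking the introducing sentence as the definition. The sizes quoted (a spurious gap of −4 to −10 under unchanged decline of 2 to 5 mL/min/1.73m² per year and one-year windows) are illustrations.

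The disagreement with the Estimated Slope further assumes that time in 2.4.2 runs forward relative to baseline, as 2.4.1 defines it; 2.4.2 does not restate it. The e-GFR slope comparison and its p-value are not affected. This should be fixed because it reverses the reported direction of one of the two efficacy items before treatment, but it does not alter the tested result.

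**What to change.** In SAP 2.4.2, item 2:

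- Write Pre-administration change = (Baseline − Pre-baseline value).
- Keep Post-administration change = (Post-administration value − Baseline).
- State, in the text and as a table footnote, that a negative value means decline in both periods.

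Since the intervals before and after baseline can differ in length, it also helps to label both changes as descriptive and not annualised, and to refer readers to the Estimated Slopes for the per-year comparison. Dividing each change by its interval is not needed to correct the sign. It would also add noise at short intervals: 0.1 year multiplies measurement error by 1/0.1 = 10.

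The cost is one formula line, one footnote and a re-run of the descriptive e-GFR change output. The mixed model does not change.
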